## 2 Statistical Hypotheses

As depicted in the study protocol, a 2-stage conditional sequence of statistical hypothesis tests, will be used. The testing sequence will be as follows:

- Stage 1: Four concurrent analyses will be done:
  - A-study analysis of co-primary variables:
    - ADAS-cog is analyzed in A-study.
    - CDR-sb is analyzed in A-study
  - B-study analysis of co-primary variables:
    - ADAS-cog is analyzed in B-study.
    - CDR-sb is analyzed in B-study
- Stage 2: Conditional on statistical significance of both A-study and B-study in both co- primary variables, testing will continue:
  - MRI assessment is analyzed in the study (as a whole) Stage 2:
- Stage 3: Conditional on statistical significance in both stage 1 and stage 2 testing will continue:
- All other secondary endpoints will be evaluated in a hierarchical manner in the combined total of subjects in the 2 studies

For simplicity in notation, thresholds for significance are indicated as “ $p < 0.05$ ”; however, “0.05” is representative of the alpha allocated to the analysis. The overall study-wise alpha is 0.05, but particular analyses may have alpha less than 0.05.

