### STAGE 3:

If all hypotheses defined in both Stage 1 and Stage 2 demonstrate statistical superiority of azeliragon TTP488 5 mg added to SoC versus placebo added to SoC, the secondary efficacy endpoints will be tested in hierarchical order. The order of testing is defined in [Section 4.1](#) (efficacy variables). The outline of the hierarchical testing is:

- First, the secondary endpoint ranked as #1 will be compared between azeliragon TTP488 5 mg added to SoC versus placebo added to SoC in the study as a whole (study A and study B combined). If  $p < 0.05$ , statistical significance will be declared.
- Secondly, if the secondary endpoint ranked as #1 showed a statistically significant difference, the secondary endpoint ranked as #2 will be compared between azeliragon 5 mg added to SoC versus placebo added to SoC in the study as a whole (study A and study B combined). If  $p < 0.05$ , statistical significance will be declared.

The hierarchical testing will continue with the consecutive secondary endpoints, as long as the previous secondary endpoint is declared as statistically significant.

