#### 4.1.3 Secondary Variables

The following secondary efficacy endpoints will be evaluated in hierarchical order:

- Secondary endpoint ranked as #1: The change from baseline to final visit in the ADCS-ADL scale through Month 18.
- Secondary endpoint ranked as #2: Change from Baseline in the Neuropsychiatric Inventory (NPI) total score at Month 18.
- Secondary endpoint ranked as #3: The change from baseline to final visit in the Mini-Mental State Examination (MMSE) through Month 18.
- Secondary endpoint ranked as #4: Change from Baseline on the Trail Making Test Version A time at Month 18.
- Secondary endpoint ranked as #5: Change from Baseline on the Trail Making Test Version B time at Month 18.
- Secondary endpoint ranked as #6: Change from Baseline on the Continuous Oral Word Association Task (COWAT) score at Month 18.
- Secondary endpoint ranked as #7: Change from Baseline on the Category Fluency Test (CFT) score at Month 18.

- Secondary endpoint ranked as # 8: Change from Baseline in the Dementia Quality of Life (DEMQOL) -Proxy total score at Month 18.

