#### 4.1.5.9 Dementia Quality of Life (DEMQOL) – Proxy:

- Range: The scale range is 31—124, with lower scores indicate greater impairment.
- Brief description: The DEMQOL-Proxy questionnaire is a validated and reliable questionnaire that is interview administered and completed by the caregiver about the patient’s health related quality of life ([Smith et al, 2005](#)). It consists of 31 items representing 5 domains (daily activities and looking after oneself, health and well-being, cognitive functioning, social relationships, and self-concept) and takes approximately 20 minutes to complete. Higher scores indicate better health-related quality of life. This scale will be administered at Baseline and at Months 6, 12 and 18 or in the event of early termination. Item 32 is a global quality of life question that elicits an overall assessment of the patient’s general quality of life.

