## 5.2.2 Statistical Methods for Secondary Variables

Secondary and exploratory endpoints that are measurement variables will use similar statistical methodology to the methodology used for primary analysis. Stratification for A-study and B-study will be done as for primary variables. Efficacy variables that are proportions will be analyzed using Mantel-Haenszel test, controlling for Stratum, if appropriate. For the analysis of the categories for responders, a Cochran-Mantel-Haenszel test will be used. Methodologies for variables that are proportions will include construction of confidence intervals for each group and for the difference between groups. For analysis, Fisher's exact test will be used for single-population analysis, and a Mantel-Haenszel test will be used for analyses combining data across strata.

Responders based on the ADAS-cog total score, will be assessed using cumulative percentage plots. Similarly, responders based on the CDR-sb score will be assessed using cumulative percentage plots. The y-axis will show the cumulative percentage of patients who achieved the specific measure of improvement in the ADAS-cog (or CDR-sb) total score shown on the x-axis with a separate cumulative percentage curve for each treatment group.

The proportion of participants who experience loss of one global stage on the CDR will be assessed at each Visit using logistic regression with treatment (as a categorical/class variable), and baseline CDR global score (as a continuous variable). Summary measures from the analysis will include the odds ratio, 95% confidence interval for the odds ratio, and p-value for treatment comparison. Additionally, the proportion of participants in each CDR global stage will be presented.

Kaplan-Meier plots will be provided for each time-to-event variable. For each day, the "survival probability" will be computed by the product-limit method. Time-to-event endpoints may be modelled using Cox proportional hazards models with fixed effects for treatment and baseline measures as a covariate for supportive purposes. The estimated hazard ratio between Azeliragon and placebo will be presented with associated p-values and 95% confidence intervals.

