Time to loss of one global stage on the global CDR will include Kaplan-Meier curves. Survival estimates for treatment groups will be compared using the logrank statistic. Observations will be treated as right censored for participants who complete the study without a loss of one stage on the global CDR score or who discontinue the study prematurely.

Subgroup analyses will be done as identified subsequently; data-driven subgroup analyses may be done as exploratory analyses.

For change from Baseline in plasma concentrations of A $\beta$  species, an MMRM analysis similar to that described for the co-primary endpoints with baseline plasma concentrations of A $\beta$  species as a continuous covariate will be performed. Transformation using logarithms may be needed, depending on the distribution.

For change from Baseline in MMSE, an MMRM analysis similar to that described for the co-primary endpoints will be performed, with baseline MMSE as a continuous covariate.

For change from Baseline in NPI, an MMRM analysis similar to that described for the co-primary endpoints will be performed, with baseline NPI as a continuous covariate.

Individual item responses on the RUD questionnaire and the total caregiver time spent assisting the patient based on the RUD questionnaire will be summarized by treatment group.

For change from baseline in DEMQOL-Proxy total score, an ANCOVA analysis with Baseline DEMQOL-Proxy as a continuous covariate will be performed.

If the distribution of any of the above parameters, key secondary, or other secondary endpoints does not appear to be normally distributed, the rank analogues will be utilized.

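### DEMQOL-Proxy, the last ranked secondary, is assigned an ANCOVA although its three post-baseline visits would support the trial's own MMRM

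*SAP*

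**What the plan says.** SAP 4.1.3 places the endpoint at the end of the ranked list: "Secondary endpoint ranked as # 8: Change from Baseline in the Dementia Quality of Life (DEMQOL) -Proxy total score at Month 18". Under Stage 3 of SAP section 2, once Stages 1 and 2 have succeeded, "the secondary efficacy endpoints will be tested in hierarchical order".

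SAP 4.1.5.9 gives the measurement schedule: "This scale will be administered at Baseline and at Months 6, 12 and 18 or in the event of early termination".

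SAP 5.2.2 sets the general rule: "Secondary and exploratory endpoints that are measurement variables will use similar statistical methodology to the methodology used for primary analysis". The primary methodology in SAP 5.2.1 is an MMRM. The same section names an MMRM explicitly for plasma Aβ, NPI and MMSE, for example: "For change from Baseline in MMSE, an MMRM analysis similar to that described for the co-primary endpoints will be performed". ADCS-ADL, Trail Making A and B, COWAT and CFT have no sentence of their own and fall under the general rule.

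DEMQOL-Proxy is the only ranked scale with a different instruction: "For change from baseline in DEMQOL-Proxy total score, an ANCOVA analysis with Baseline DEMQOL-Proxy as a continuous covariate will be performed". Protocol 9.5.3 carries the same sentence. In the protocol the testing sequence stops at the MRI endpoint. The SAP added Stage 3, made DEMQOL-Proxy a ranked test and left the sentence unchanged.

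**The concern.** The section states a rule and then departs from it for one scale without explanation. SAP 5.2.1 says its ANCOVA models draw on baseline and Month 18 data, and SAP 6.2 makes no imputation the default. Taken together, a patient who gives DEMQOL-Proxy scores at Months 6 and 12 and then leaves contributes nothing to the Month 18 test.

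Two things are at stake:

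- **Assumption.** An observed-case ANCOVA relies on dropout being unrelated to the Month 18 outcome given treatment and the baseline covariates. The MMRM also allows dropout to depend on the Month 6 and 12 scores.
- **Precision.** The intermediate scores of dropouts carry some information about Month 18, and the ANCOVA does not use it.

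A second reading is open. SAP 6.2 also says that a withdrawn patient's final assessment serves as the endpoint value where applicable, so the ANCOVA could be run on carried-forward data. That would use the earlier scores, but under an assumption of no change after withdrawal, which is no better in a progressive disease.

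**Working it through.** The documents give no SD, effect size, correlation or power for DEMQOL-Proxy, so there is no stated figure to reproduce. Everything below about this scale is illustrative.

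**Inputs from the documents.** About 800 randomized (SAP 1.4); dropout of 20% or less (SAP 1.6); post-baseline visits at Months 6, 12 and 18 (SAP 4.1.5.9). At 20% dropout, 800 × 0.20 = 160 patients have no Month 18 score and 640 do.

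**Assumptions.** Dropout is spread evenly, 6.67% in each of the three intervals. The fractions observed are then f6 = 0.9333, f12 = 0.8667 and f18 = 0.80. The score has unit variance, with adjacent-visit correlation ρ from 0.5 to 0.8. Both models adjust for baseline.

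**Precision, first-order autoregressive correlation.** Given baseline, the variances of the estimated means, per patient randomized, are:

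- Month 6: v6 = (1 − ρ²)/f6
- Month 12: v12 = (1 − ρ²)/f12 + ρ²·v6
- Month 18, MMRM: v18 = (1 − ρ²)/f18 + ρ²·v12
- Month 18, observed-case ANCOVA: (1 − ρ⁶)/f18

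For ρ = 0.7:

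- v6 = 0.51/0.9333 = 0.5464
- v12 = 0.51/0.8667 + 0.49 × 0.5464 = 0.8562
- v18 = 0.51/0.80 + 0.49 × 0.8562 = 1.0570
- ANCOVA = 0.8824/0.80 = 1.1029
- Ratio = 1.0570/1.1029 = 0.958

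**Precision, exchangeable correlation.** Given baseline, each visit has variance 1 − ρ² and each pair of visits covariance ρ − ρ². The MMRM variance is the Month 18 element of the inverse of the information summed over the dropout patterns.

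| ρ | MMRM/ANCOVA variance, autoregressive | Exchangeable |
|---|---|---|
| 0.5 | 0.979 | 0.980 |
| 0.6 | 0.969 | 0.975 |
| 0.7 | 0.958 | 0.970 |
| 0.8 | 0.947 | 0.966 |

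The MMRM variance is therefore about 2% to 5% lower in the first case and 2% to 3% lower in the second.

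**Bias, by simulation.** 800 patients, 1,500 replicates per scenario, assumed effect 0.2 SD, autoregressive correlation 0.6, 0.75 or 0.9, dropout about 17% to 20%. Bias in SD units:

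| Dropout mechanism | Observed-case ANCOVA | LOCF ANCOVA | MMRM-type estimate |
|---|---|---|---|
| Completely at random | within 0.002 | −0.012 to −0.015 | within 0.002 |
| Depends on last score, same in both arms | within 0.003 | −0.007 to −0.013 | within 0.005 |
| Depends on last score, one arm only | −0.036 to +0.033 | −0.061 to +0.034 | within 0.002 |

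The largest observed-case bias, 0.036, is 18% of the assumed effect (0.036/0.2). The ratio of ANCOVA to MMRM standard error was 1.00 to 1.04 in all scenarios, which agrees with the analytic result.

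**The case against.** The strongest case for leaving the plan alone is that it is a deliberate, prespecified choice. Protocol and SAP agree on it, a specific sentence overrides a general one, and the general rule asks only for similar methodology. ANCOVA at one timepoint is a valid test of a Month 18 endpoint. All of that stands. It shows that the plan is permissible, but not that it is the better use of three planned visits.

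Four stronger readings might be inferred, and the documents do not support them:

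- **That the model adjusts for baseline only.** The sentence names only baseline, but so do the MMSE and NPI sentences. SAP 5.2 puts the randomization stratum in efficacy analyses, SAP 5.2.1 puts it in the ANCOVA models, and SAP 5.2.2 stratifies secondaries by A-study and B-study.
- **That only completers can enter.** SAP 6.5 maps early-termination efficacy data to the nearest scheduled visit, so some non-completers obtain a Month 18 value. The final-assessment clause in SAP 6.2 could admit others. SAP 4.1.4 also lists the Month 6 and 12 changes as analysis variables, so those scores are analysed, though not in the Month 18 test.
- **That the ANCOVA is biased whenever dropout depends on outcome.** The simulation shows negligible observed-case bias when the same mechanism acts in both arms. Bias appeared only when the mechanism differed by arm.
- **That the precision gain approaches 8%.** With autoregressive correlation, leaving baseline out of both models gives ratios of 0.977, 0.964, 0.946 and 0.924. Both planned models adjust for baseline, so that comparison does not apply.

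The objection that the consequence is slight also stands. DEMQOL-Proxy is tested only after four co-primary tests, hippocampal volume and seven other secondaries have all succeeded, and no later test depends on it.

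**Conclusion.** The point holds as a small improvement that costs almost nothing. The SAP gives its last ranked scale an unexplained ANCOVA when its own general rule, and the data it already plans to collect, support an MMRM. On the observed-case reading, the Month 18 test leaves out dropouts' Month 6 and 12 scores and relies on a stronger missing-data assumption. The LOCF-type reading is no better.

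The size is modest: about 2% to 5% lower variance at 20% dropout, and removal of a bias of up to about 0.04 SD (observed cases) or 0.06 SD (LOCF) if outcome-dependent dropout differs between arms. These figures rest on assumed correlations, dropout patterns and effect size, because the documents give none for this scale. The MMRM's advantage on bias also requires that missingness be explained by the observed scores and model covariates.

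Nothing here affects type I error control, the co-primary endpoints or any other ranked test.

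**What to change.** In SAP 5.2.2, replace the DEMQOL-Proxy sentence with the primary-type MMRM: change from baseline at Months 6, 12 and 18; treatment, visit and treatment-by-visit terms; baseline DEMQOL-Proxy, randomization stratum and A/B-study terms; and the Month 18 treatment contrast as the ranked test. Keep the ANCOVA as a supportive analysis and state whether it uses observed cases or carried-forward values. The same MMRM would supply the Month 6 and 12 contrasts for the changes already listed in SAP 4.1.4.

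The cost is a wording change before unblinding, plus a line recording the departure from protocol 9.5.3. No extra visits, data or patients are needed.

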For change from Baseline in plasma concentrations of A β species, an MMRM analysis similar to that described for the co-primary endpoints with baseline plasma concentrations of A β species as a continuous covariate will be performed.

For change from Baseline in NPI and MMSE, an MMRM analysis similar to that described for the co-primary endpoints with baseline NPI, and MMSE, as a continuous covariate, respectively, will be performed.

Individual item responses on the RUD Lite questionnaire and the total caregiver/informant time spent assisting the patient based on the RUD Lite questionnaire will be summarized by treatment group.

For change from baseline in DEMQOL-Proxy total score, an ANCOVA analysis with Baseline DEMQOL-Proxy as a continuous covariate will be performed.

If the distribution of any of the above parameters, key secondary, or other secondary endpoints does not appear to be normally distributed, the rank analogues will be utilized.

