**STAGE 2:**

If and only if both hypothesis tests in A-study AD subjects and also B-study AD subjects for both co-primary variables (ADAS-cog and CDR-sb) have  $p < 0.05$  (i.e.,  $p < 0.05$  for ADAS-cog demonstrating statistical superiority of azeliragon 5 mg added to SoC versus placebo added to SoC and also  $p < 0.05$  for CDR-sb demonstrating statistical superiority of azeliragon 5 mg added to SoC versus placebo added to SoC (i.e., statistical significance of the test of the null hypothesis for each A-study and B-study independently), testing will proceed to the fifth set of hypotheses to the expansion of the population of subjects from A-study and B-study combined.

Consistent with the FDA draft Guidance for Industry: *Alzheimer's Disease: Developing Drugs for the Treatment of Early Stage Disease* (February, 2012), toward the goal of demonstrating disease modification, analysis of MRI data (hippocampal volume as the key secondary endpoint) will be done conditional on significance of the above-named hypothesis tests:

The next set of hypotheses to be tested is as follows:

- $H_{05}: \mu^{(MRI, \text{azeliragon, All})} = \mu^{(MRI, P, All)}$
- $H_{15}: \mu^{(MRI, \text{azeliragon, All})} \neq \mu^{(MRI, P, All)}$

where  $\mu^{(MRI, \text{azeliragon, All})}$  and  $\mu^{(MRI, P, All)}$  denote the true mean changes from Baseline at Month 18 on MRI volume measures for all AD azeliragon 5 mg/day and placebo groups, respectively.

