#### 4.1.2 Key Secondary Variables of Analysis (Imaging)

The key secondary endpoint is:

- Change from Baseline in hippocampal volume at Month 18.

PET variables are considered to be exploratory and will be defined separately.

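### The confirmatory secondary tests can be replaced by unnamed rank methods on an undefined judgement of normality, and for hippocampal volume this contradicts SAP 5.2.4

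*SAP*

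**What the plan says.** The rule closes SAP 5.2.2. Its list of endpoints ends with the key secondary and other "secondary endpoints does not appear to be normally distributed, the rank analogues will be utilized". Protocol 9.5.3 has the same condition and consequence: "does not appear to be normally distributed, the rank analogues will be utilized".

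The endpoints it covers carry formal tests.

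- **Stage 2.** SAP 4.1.2 names the key secondary as "Change from Baseline in hippocampal volume at Month 18". SAP section 2 makes it a gated test: "analysis of MRI data (hippocampal volume as the key secondary endpoint) will be done conditional on significance of the above-named hypothesis tests". The parameters in H05 and H15 "denote the true mean changes from Baseline at Month 18 on MRI volume measures for all AD azeliragon 5 mg/day and placebo groups".
- **Stage 3.** If Stages 1 and 2 succeed, "the secondary efficacy endpoints will be tested in hierarchical order". SAP 4.1.3 ranks eight of them. The stopping rule is: "The hierarchical testing will continue with the consecutive secondary endpoints, as long as the previous secondary endpoint is declared as statistically significant".

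The planned methods are mean-based. Under SAP 5.2.2, measurement endpoints follow the primary method (MMRM), except DEMQOL-Proxy, which has ANCOVA. SAP 5.2.4 gives MRI a main-effects ANCOVA on change from baseline, adjusted for skull size, and lists rank ANCOVA as supportive. For the co-primaries, SAP 5.2.1 also keeps rank methods (Wilcoxon, rank ANCOVA, van Elteren) supportive.

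**The concern.** A fixed testing sequence relies on each link having one test, named in advance. Here the mean-based test is not supplemented but replaced, and what triggers the replacement is left open. The SAP does not say:

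- which normality test or cut-off applies;
- whether raw changes or model residuals are inspected;
- who decides, when, and whether blinded;
- which rank method takes over.

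Three things are at stake. First, the hypothesis: H05 concerns mean changes, and a rank test answers a different question. Second, missing data: none of the rank methods named in SAP 5.2.1 is a repeated-measures method, so an endpoint moved off MMRM loses that handling of dropouts. SAP 6.2 has a general convention that a withdrawn subject's last assessment serves as the endpoint value where applicable, but nothing ties it to the rank tests. Third, freedom of choice: where two or more p-values are available and no rule decides between them, the nominal level is not guaranteed.

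**Working it through.** **1. The plan's own figures.** The documents give no operating characteristic for the switch and no power for any secondary endpoint. The figures nearby do reproduce: 2 × ⌈141/0.8⌉ = 354 for ADAS-cog, 304/0.8 = 380 for CDR-sb, and 0.05 − 10 × 0.0001 = 0.049 for the co-primary alpha. None of them bears on this rule.

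**2. The passages side by side.** For hippocampal volume, SAP 5.2.2 makes the rank analogue the replacement if normality appears to fail, while SAP 5.2.4 makes ANCOVA the analysis and rank ANCOVA supportive. The specific section does not simply override the general one: 5.2.4 also says the MRI methodology resembles that for the other secondary variables, and 5.2.2 names the key secondary outright. The text does not settle which governs.

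**3. Search for a trigger elsewhere.** The SAP introduction says the plan was finalized after the final blind data review meeting, yet the rule is still open. SAP 6.2 leaves to blind review only the methods for missing-data sensitivity analyses. Protocol 11.1 has each sub-study locked, unblinded and analysed as it completes, while the secondaries pool A and B. The pooled distributions could therefore be judged after A-study is unblinded; the documents neither require nor exclude this.

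**4. Type I error under no effect.** Assumptions: 320 per arm (800 × 0.8 / 2), unadjusted two-sample t-test against the same test on ranks, 20,000 runs per distribution, nominal level 0.05. The fixed rule uses the rank test when a Jarque-Bera test on residuals about each arm's mean has p < 0.05, and the t-test otherwise. The Monte Carlo standard error is √(0.05 × 0.95 / 20,000) = 0.0015.

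| Null distribution | Mean test | Rank test | Tests disagree | Fixed rule | Either p < 0.05 |
|---|---|---|---|---|---|
| Normal | 0.05025 | 0.04965 | 0.01940 | 0.05075 | 0.05965 |
| t, 5 df | 0.05115 | 0.04990 | 0.03585 | 0.04990 | 0.06845 |
| Lognormal, σ = 0.5 | 0.05090 | 0.04960 | 0.04080 | 0.04960 | 0.07065 |
| t, 3 df | 0.04845 | 0.05110 | 0.04665 | 0.05110 | 0.07310 |

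The last column follows from P(either) = [P(mean) + P(rank) + P(disagree)] / 2. For the normal case this is (0.05025 + 0.04965 + 0.01940) / 2 = 0.05965.

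Other assumed shapes, with 8,000 runs, gave ceilings of up to 8.4% (a lognormal). With the normality check applied to pooled data instead (6,000 runs), the fixed rule rejected 4.6 to 4.8% of the time for non-normal shapes and 5.1% for normal data.

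**5. Whether the two tests ask the same question.** Equal means, different shapes, 320 per arm, 5,000 runs:

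- Normal(0, 1) against exponential(1) − 1, both with mean 0: the mean test rejects 5.4%, the rank test 37.8%.
- Normal(0, 1) against Normal(0, 1) − 0.25 with 10% of patients shifted by +2.5, so the mean is −0.25 + 0.1 × 2.5 = 0: the mean test rejects 4.9%, the rank test 13.5%.

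In both cases H05 as written is true, yet the rank test rejects far above 5%. A rank rejection is therefore not evidence against H05.

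**The case against.** The best defence is that the clause depends on the shape of the data, not on the result, and that it is mandatory. If an endpoint is clearly non-normal, the rank test is compelled and no favourable choice remains. Discretion is greatest for borderline-normal data, where the ceiling is lowest (6.0%). This stands as far as type I error goes: the fixed rule held 5.0 to 5.1% in the table above. It does not answer the change of hypothesis, which occurs even if the rule is mechanical and blinded. Nor does it tell the analyst which rank method to use.

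Several stronger readings are tempting but not supported:

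- *The Stage 2 test will switch to ranks.* SAP 5.2.4 says otherwise for MRI, so this is an unresolved contradiction.
- *Error is inflated to 6 to 8%.* That requires the choice to follow the p-value, which the clause does not prescribe. The simulated tests also omit the baseline and stratum adjustment that the plan uses.
- *Every switch loses repeated-measures handling.* Hippocampal volume and DEMQOL-Proxy are already analysed by ANCOVA.
- *NPI and Trail Making are skewed, so the clause will be invoked.* The Trail Making caps (150 and 300 seconds) make non-normality plausible, but the analysed variable is change from baseline and the documents give no distributions.

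It is also fair to say that Stages 2 and 3 open only if all four co-primary tests succeed.

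**Conclusion.** The point holds as a defect of specification in confirmatory tests. The trigger and the replacement are undefined, the rule conflicts with SAP 5.2.4 for the key secondary, and following it would test something other than the stated mean hypothesis. For the MMRM endpoints a switch would also leave the treatment of missing Month 18 values unstated.

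The type I error consequence is a risk, not a finding. The error is near 5% if a rule is fixed and applied consistently, with a ceiling of about 6 to 8% per test if the choice follows the result. Within a fixed sequence that ceiling applies to the first true null hypothesis reached, so it does not accumulate over the nine links. The figures rest on unadjusted tests, assumed distributions and 320 per arm, and are illustrative. A reader might infer that the main efficacy conclusion is in doubt. It is not: rank methods are supportive only for ADAS-cog and CDR-sb.

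**What to change.** Before any unblinding:

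1. Delete the sentence from SAP 5.2.2, so that it agrees with 5.2.4.
2. State one confirmatory test per endpoint, whatever the distribution: ANCOVA for hippocampal volume and DEMQOL-Proxy, MMRM for the other seven ranked secondaries. Rank ANCOVA or van Elteren then serve as sensitivity analyses only.
3. If a rank test is preferred for a particular endpoint, such as NPI or Trail Making, name that test and its missing-data handling now, and word its hypothesis to match.
4. List the departure from protocol 9.5.3 in SAP 1.9, which at present records only the removal of Bazett's correction.

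A numerical normality rule on blinded pooled data would protect the error rate but leave the hypothesis dependent on the data, so it is the weaker remedy.

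The cost is a tracked SAP amendment; protocol 9.0 lets the SAP supersede the protocol. The sample size does not change. The fixed mean-based test held 4.8 to 5.1% in all four distributions tried, so the switch is not needed for validity at this size. Some efficiency may be lost if an endpoint proves heavy-tailed.
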